## 10. PHARMACOKINETICS

### 10.1. Graphical and Tabular Summaries of Pharmacokinetic Profiles

The PK Population will be used when summarizing plasma PK concentrations. Participants enrolled who did not complete dosing will not be included in the PK analysis but will have concentration and PK parameters included in listings as appropriate.

Concentrations below the limit of quantification (BQL) collected before the first measurable concentration above the lower limit of quantification (LLOQ) will be treated as zero (0) for plotting and all calculations (including noncompartmental analysis [NCA]) and summary statistics. All other BQL values observed after the first measurable concentration will be treated as missing. There will be no imputation of missing concentrations. The geometric mean (GM) of concentrations will be treated as missing for sets of data points containing a BQL value.

Collection of plasma samples outside of the protocol-defined time window for the time point will not result in exclusion of the sample results from NCA. Plasma samples collected out of window will be evaluated on a case-by-case basis. Results from PK samples that were collected substantially outside of the protocol-defined time window will be excluded from concentration summary statistics by nominal time points and plots of mean concentration by nominal time point. Substantially out of window samples are defined as samples that were collected outside twice the size of the protocol required window, and are as follows: >10 minutes after the completion of the infusion;  $\pm 20$  minutes in the first 8 hours after dosing;  $\pm 1$  hour between 9 and 72 hours after dosing;  $\pm 2$  days on Day 7;  $\pm 4$  days on Day 14;  $\pm 8$  days on Day 28 and Day 56; and  $\pm 14$  days on Day 84, Day 112, and Day 150.

If the exact time of the PK sample collection is not recorded, then the collection time will be imputed as the planned time for analysis if it is not known that the sample was collected outside of the protocol-defined time window. If the exact collection time is not known, but it is known that the sample was collected outside of the protocol-defined time window, then the time point may be excluded from analysis at the discretion of the PK analyst. Rationale for excluding results from analysis will be described in the CSR. Results from samples with imputed collection times will be indicated in listings of PK sample concentrations.

The bioanalytical lab will report plasma concentrations in units of  $\mu\text{g}/\text{mL}$ . Plasma drug concentrations will be summarized and listed by participant in [Listing 10](#). This listing will include separate columns for concentrations reported by the lab and concentrations used for analysis. The lab reported concentrations may include codes, such as: "BQL" or "QNS" (Quantity not Sufficient), while the analysis concentrations will contain numeric data only, including imputed values such as 0 for pre-dose time points and BQL samples prior to the first quantifiable sample. It will also indicate the nominal time (i.e., the planned time) and actual post dose time in hours associated with the sample and will note sample times which were collected out of window, substantially out of window, or imputed.

Individual concentrations will be presented in tables and figures by dose group and nominal time point:

- The GM and coefficient of variation as a percent (CV%) of individual concentrations in plasma will be presented tabularly by Treatment Group ([Table 16](#) for sampling times between 0 and 72 hours post dose and [Table 17](#) for sampling times between Day 7 and Day 150).
- Individual concentrations in plasma and summary statistics, including mean, SD, min, max, GM, and CV%, will be presented tabularly for each Treatment Group beginning at [Table 18](#) and continuing through [Table 27](#).

- Individual concentration profiles in plasma will be presented graphically by Treatment Group for 0 to 72 hours post dose and across all post dose sampling time points in **Figure 3** and **Figure 4**, respectively.
- Semi-log individual concentration profiles in plasma will be presented graphically by Treatment Group for 0 to 72 hours post dose and across all sampling time points in **Figure 5** and **Figure 6**, respectively.
- Mean concentration profiles in plasma with error bars presenting  $\pm 1$  SD around each time point will be presented graphically by Treatment Group for 0 to 72 hours post dose and across all post dose sampling time points in **Figure 7** and **Figure 8**, respectively.
- Semi-log mean concentration profiles in plasma with error bars presenting  $\pm 1$  SD around each time point will be presented graphically by Treatment Group for 0 to 72 hours post dose and across all post dose sampling time points in **Figure 9** and **Figure 10**, respectively.

The CV% will be calculated using the method for log-normally distributed data:

$$CV\% = \sqrt{\exp(s^2) - 1} \times 100\%,$$

where  $s^2$  is the variable of the natural log-transformed data.

## 10.2. Noncompartmental Analysis

PK parameters from plasma PK data will be estimated through NCA using version 8.3.4 or higher of Phoenix WinNonlin®. Actual post dose times will be used for the estimate of PK parameters instead of nominal time. In the case of imputed sample collection times, the imputed time will be included in the NCA. Any outlier identified in the PK analysis will be discussed in the CSR. Outliers will not be excluded from the PK analysis.

Individual plasma PK parameter estimates will be listed (**Listing 11**). PK parameters will be summarized and presented tabularly for all Treatment Groups (**Table 28**). Detailed summary statistics of each PK parameter will be presented tabularly for each Treatment Group (beginning at **Table 29** and continuing through **Table 33**). Summary statistics will include mean, SD, min, max, GM, and CV%.

Phoenix WinNonlin NCA will use the following settings to compute parameters from plasma PK data:

- Linear Up Log Down calculation method
- Uniform weighting
- IV infusion
- Lambda Z Acceptance Criteria
  - $Rsq\_adjusted \geq 0.90$
  - Include at least 3 time points after  $T_{max}$

If an insufficient number of participants meet the Lambda Z Acceptance Criteria for computing plasma PK parameters, then relaxed criteria may be used and will be described in the CSR.

### **Cmax**

Cmax is defined as the maximum concentration observed over all PK sample concentrations. It will be obtained from the Cmax parameter calculated by WinNonlin. If there are no measurable concentrations in the

participant's PK profile, then  $C_{\max}$  will be missing for that participant.  $C_{\max}$  will be reported in units of  $\mu\text{g/mL}$ . The dose-normalized parameter  $C_{\max}/\text{Dose}$  will also be reported from the **Cmax\_D** parameter calculated by WinNonlin with units  $(\mu\text{g/mL})/(\text{mg/kg})$ .

#### **Cmin**

$C_{\min}$  is defined as the minimum concentration observed over all PK sample concentrations. It will be obtained from the **Cmin** parameter calculated by WinNonlin. If there are no measurable concentrations in the participant's PK profile, then  $C_{\min}$  will be missing for that participant.  $C_{\min}$  will be reported in units of  $\mu\text{g/mL}$ .

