#### 4.5.2. Pharmacokinetics Variables

SAR440894 plasma concentrations will be determined using a validated enzyme-linked immunosorbent assay. PK samples will be analyzed by Aptuit (Verona) Srl. PK sample collections will be performed at the following time points: Baseline pre-infusion (60 to 0 minutes prior to start of infusion), at the completion of the infusion, and at (relative to the end of the infusion), 1, 4, 8, 12, 24, 48, and 72 hours, and on Day  $7 \pm 1$ , Day  $14 \pm 2$ , Day  $28 \pm 4$ , Day  $56 \pm 4$ , Day  $84 \pm 7$ , Day  $112 \pm 7$ , Day  $150 \pm 7$ , and ET (if needed). For blood sample collection, there will be an acceptable window of  $\pm 10$  minutes in the first 8 hours after dosing and  $\pm 30$  minutes between 9 and 72 hours. PK samples at Follow-up visits will be collected during the designated Follow-up window. The “end of infusion” sample should be obtained within 5 minutes of the end of the infusion.

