### **6.3.2. Pharmacokinetics Population**

The PK Population will include all participants who received a complete dose of SAR440894 and have at least one quantifiable post-dose plasma drug concentration record.

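### As written, Cmin takes in the pre-dose sample, so it is 0 for essentially every active participant and its table entries carry no information

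*SAP*

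**What the plan says.** Protocol 10.5.2 names Cmin among the PK parameters and does not say which samples it covers. SAP 10.2 supplies the definition: Cmin "is defined as the minimum concentration observed over all PK sample concentrations". On the source of the value it adds: "It will be obtained from the Cmin parameter calculated by WinNonlin". The only exception is a profile with no measurable concentration at all, for which Cmin is missing.

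The following SAP sections determine the result:

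- SAP 4.5.2 puts the pre-infusion draw first in the sampling list: "PK sample collections will be performed at the following time points: Baseline pre-infusion (60 to 0 minutes prior to start of infusion".
- SAP 10.1 says that BQL results "collected before the first measurable concentration above the lower limit of quantification (LLOQ) will be treated as zero (0) for plotting and all calculations", and states that this covers NCA and the summaries: "including noncompartmental analysis [NCA]) and summary statistics". Its description of Listing 10 confirms that pre-dose time points carry a 0 in the analysis column.
- SAP 10.1 on later BQL results: "All other BQL values observed after the first measurable concentration will be treated as missing".
- SAP 10.1 on geometric means: "The geometric mean (GM) of concentrations will be treated as missing for sets of data points containing a BQL value".
- SAP 6.3.2 limits the PK Population to participants who had a complete dose and "have at least one quantifiable post-dose plasma drug concentration record".

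Table 28 shows Cmin as GM (CV%). Tables 29 to 33 show mean, SD, GM, CV%, minimum and maximum for each dose. SAP 10.1 calculates CV% from the variance of the log-transformed values.

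**The concern.** After a single dose, a useful Cmin describes how far the concentration has fallen by the end of sampling. A minimum that can be taken at the pre-dose draw describes the state before any drug was given. It is the same at every dose level and says nothing about exposure. The protocol names this parameter, yet the tables meant to report it would hold only zeros and statistics that cannot be calculated.

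A partial failure would be harder to see. If one participant in a group lacks a pre-dose sample, that group's Cmin mixes pre-dose zeros with one real post-dose concentration, and the resulting mean describes neither.

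**Working it through.** **Inputs.** SAP Table 1 plans 6 active participants in each of 5 cohorts: 5 × 6 = 30 active, and 5 × 8 = 40 in all, which matches the plan. The expected half-life is about 4 weeks (Protocol 2.1). The documents give no LLOQ.

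**Step 1: does the zero rule apply?** Everyone in the PK Population has a quantifiable post-dose value. A BQL pre-dose sample therefore always precedes a measurable one and is set to 0. For the same reason, the exception for profiles with nothing measurable cannot arise in Tables 28 to 33.

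**Step 2: how often is pre-dose BQL?** This is an inference. No clinical study of the product preceded this one (Protocol 2.2.2) and each participant has one dose. Exclusion criteria 26 and 28 remove people with anti-CHIKV antibodies and recent recipients of monoclonal antibodies. The exceptions would be a missing pre-dose sample or an unexpected quantifiable one.

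**Step 3: the minimum.** Concentrations are never negative, so min(0, post-dose values) = 0. Simulated one-compartment profiles (6 per dose, 5 doses; assumed half-life 21, 28 or 35 days; assumed LLOQ 0.01, 0.1 or 0.5 µg/mL) gave Cmin = 0 for every participant in all nine settings. This only confirms the logic of the written rule.

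**Step 4: the statistics.** For six zeros, mean = SD = minimum = maximum = 0. CV% = √(exp(s²) − 1) × 100% needs ln(0), so it is undefined. GM is 0, or missing if the rule written for concentrations is taken to cover Cmin.

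**Step 5: cells affected.**

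- Table 28: 1 row × 5 groups = 5.
- Tables 29 to 33: 6 statistics × 5 tables = 30.
- Parameters affected: 1 of the 11 in Table 28.

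**Step 6: one missing pre-dose sample in a group of six.** The values are (0, 0, 0, 0, 0, x), where x is that participant's lowest post-dose value.

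- Mean = x/6 = 0.167x.
- SD = √[(x² − x²/6)/5] = x/√6 = 0.408x.
- SD/mean = √6 = 2.45, an arithmetic CV of 245%. The log-scale CV% is still undefined.

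**Step 7: would restricting Cmin to post-dose samples be enough?** It removes the zeros. A later BQL result, however, counts as missing under SAP 10.1, so an earlier and higher value would take its place. If Day 150 is BQL and Day 112 is not, with log-linear decline, the ratio of the Day 112 to the Day 150 concentration is 2^(38/t½):

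| Half-life | Ratio |
|---|---|
| 21 days (assumed) | 3.51 |
| 28 days (Protocol 2.1) | 2.56 |
| 35 days (assumed) | 2.12 |

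**Related shell points.** SAP 10.2 sends individual parameters to Listing 11. The column there that should be Cmin appears to be headed Cmean, a quantity 10.2 does not define. Separately, SAP 4.5.2 plans 1 + 1 + 7 = 9 samples to 72 h, timed from the end of infusion. Tables 16 and 18, and the four tables that follow the Table 18 format (20, 22, 24 and 26), have 8 columns: 0, 1, 4, 8, 12, 24, 48 and 72 h from dosing. Counted from the start of a 60-minute infusion, the nominal times are 0, 1, 2, 5, 9, 13, 25, 49 and 73 h, and only 0 and 1 match. Counted from the end of infusion, the pre-dose sample has no column.

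**The case against.** The strongest objection is that little is lost. Cmin is descriptive and secondary, no hypothesis test is planned, and it feeds no model or escalation rule; the ADA analysis uses clearance. Once restricted to post-dose samples, single-dose Cmin is mostly the last quantifiable concentration, which the concentration tables and Listing 10 already show. A column of zeros would be noticed at first output, and the SAP allows departures to be explained in the CSR. This stands as a limit on importance. It does not make the definition right.

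A second objection is that the printed value comes from WinNonlin and the documents do not say how that output treats a pre-dose record. That stands as uncertainty about what would be printed. If the software includes the record, the value is 0. If it leaves the record out, the output contradicts the definition beside it. The text needs correction in both cases. The exception for profiles with nothing measurable may hint that measurable values were meant, but it does not confine the minimum to post-dose samples.

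Third, some of the figures are conditional. The mixed-group result needs a missing pre-dose sample, and the 2.1- to 3.5-fold ratio needs a BQL Day 150 result, which cannot be foreseen without an LLOQ. As an illustration, with the monkey volume of 0.0706 L/kg from Protocol 2.1 and a 28-day half-life, the lowest dose gives 0.3/0.0706 × 2^(−149/28) ≈ 0.11 µg/mL at Day 150. These figures show why a rule is needed and do not predict results.

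Finally, the Listing 11 heading may be a typing slip or a misreading of the PDF, so it calls only for a check. The column count is a separate shell matter and is secondary here.

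**Conclusion.** The concern holds. Taken together, the definition of Cmin, the sampling list, the zero rule and the PK Population force Cmin = 0 wherever the pre-dose sample is BQL, which is expected for essentially all active participants. The figure of 30 is the planned number. The PK Population may differ slightly through incomplete doses or replacements.

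The damage is confined to the 35 cells counted above. Cmax, AUC, half-life, clearance and volume do not depend on this definition, and Day 150 concentrations remain in Tables 17, 19, 21, 23, 25 and 27. The missing column touches only the nominal-time concentration tables, because NCA uses actual times. This should be put right before outputs are produced, but it does not threaten the study's main conclusions. The one inference is that pre-dose samples are BQL; everything else is in the text.

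**What to change.** 1. In SAP 10.2, define Cmin as the lowest concentration among post-dose samples only. This keeps the parameter named in Protocol 10.5.2.
2. Confirm that the WinNonlin Cmin output follows that definition. If it does not, derive Cmin outside WinNonlin.
3. For Cmin, report a participant with a post-dose BQL result as below the LLOQ, and give the number of such participants per dose group. State whether GM and CV% are omitted for a group containing such values or, if not, how they are calculated.
4. Check that the Listing 11 column reads Cmin.
5. Secondary: give Tables 16, 18, 20, 22, 24 and 26 nine columns (pre-dose, end of infusion, then 1, 4, 8, 12, 24, 48 and 72 h after the end of infusion) with one stated time origin.

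The cost is SAP wording and table or listing shells. No new data or sampling is needed, and the protocol's list of PK parameters stays as it is.

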#### **Tmax**

$T_{\max}$  is defined as the time at which the  $C_{\max}$  occurs. It will be obtained from the **Tmax** parameter calculated by WinNonlin. If there is no measurement  $C_{\max}$  in the participant's PK profile, then  $T_{\max}$  will be missing for that participant.  $T_{\max}$  will be reported in units of h.

#### **$\lambda_z$**

The terminal phase elimination rate constant ( $\lambda_z$ ) is defined as the first-order rate constant describing the rate of decrease of drug concentration in the terminal phase (defined as the terminal region of the PK curve where drug follows first-order elimination kinetics).  $\lambda_z$  will be computed as the slope of the terminal region consisting of  $\geq 3$  successive points in the plot of the log-transformed concentration versus time.  $\lambda_z$  will be estimated using uniform weighting.

Time points used in the estimation of  $\lambda_z$  will be initially selected using the WinNonlin automatic algorithm. Manually chosen time points may be used at the discretion of the PK analyst after examination of the automatically chosen points in the context of the semi-log profile to improve estimation of  $\lambda_z$  on a case-by-case basis. The set of points chosen must satisfy the Lambda Z Acceptance Criteria, described above. Otherwise, the elimination rate constant and all derived parameters (apparent terminal elimination half-life [ $t_{1/2}$ ], AUC Extrapolated to Infinity [ $\text{AUC}_{(0-\infty)}$ ], clearance [CL], and volume of distribution [ $V_d$ ]) will be treated as missing.

Drug concentrations used to calculate  $\lambda_z$  will be indicated in **Listing 10**. This parameter will be obtained from the **Lambda\_z** parameter calculated by WinNonlin.  $\lambda_z$  will be reported in units of 1/h.

#### **$t_{1/2}$**

The  $t_{1/2}$  is defined as the time required for the drug or metabolite concentration to decrease by a factor of one-half in the terminal phase. The  $t_{1/2}$  can be estimated as  $\ln(2)/\lambda_z$ . It will be obtained from the **HL\_Lambda\_z** parameter calculated by WinNonlin. Half-life will be reported in units of h. If the Lambda Z Acceptance Criteria is not met,  $t_{1/2}$  will be treated as missing.

#### **AUC**

$\text{AUC}_{(0-\text{last})}$  is defined as the area under the concentration-time curve from dosing (time 0) to the time of the last measured concentration.  $\text{AUC}_{(0-\text{last})}$  will be estimated using the Linear Up Log Down calculation method and obtained from the **AUCLast** parameter calculated by WinNonlin.

$\text{AUC}_{(0-\text{inf})}$  is defined as the total area under the concentration-time curve from dosing (time 0) taken to the limit as the end time becomes arbitrarily large.  $\text{AUC}_{(0-\text{inf})}$  can be calculated by adding  $\text{AUC}_{(0-\text{last})}$  to an extrapolated value equal to the last measured concentration greater than the LLOQ divided by  $\lambda_z$ :

$$AUC_{(0-\text{inf})} = AUC_{(0-\text{last})} + \frac{C_{\text{last}}}{\lambda z},$$

where  $C_{\text{last}}$  is the last measured concentration  $\geq$  LLOQ.  $AUC_{(0-\text{inf})}$  will be obtained from the **AUCINF\_obs** parameter calculated by WinNonlin®. If the Lambda Z Acceptance Criteria are not met,  $AUC_{(0-\text{inf})}$  will be treated as missing.

%AUCex is defined as percentage of  $AUC_{(0-\text{inf})}$  obtained by extrapolation from time of the last measured concentration to infinity. %AUCex can be calculated by dividing AUC from time of the last measured concentration to infinity by  $AUC_{(0-\text{inf})}$ :

$$\%AUC_{ex} = \frac{AUC_{(0-\text{inf})} - AUC_{(0-\text{last})}}{AUC_{(0-\text{inf})}}.$$

If %AUCex is  $>20\%$  or the Lambda Z Acceptance Criteria is not met, the estimated  $AUC_{(0-\text{inf})}$  will be excluded from statistical summaries of PK parameter estimates and downstream calculations. %AUCex will be obtained from the **AUC\_%Extrap\_obs** parameter calculated by WinNonlin.

All AUCs will be reported in units of  $\mu\text{g}^*\text{h}/\text{mL}$ . The dose-normalized parameter  $AUC_{(0-\text{last})}/\text{Dose}$  will also be reported from the **AUClast\_D** parameter calculated by WinNonlin with units  $(\mu\text{g}^*\text{h}/\text{mL})/(\text{mg}/\text{kg})$ .

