## 2. INTRODUCTION

This is a Phase 1, randomized, double-blind, placebo-controlled, multi-site, single dose escalation study to evaluate the safety, PK, and immunogenicity of intravenous (IV) SAR440894 in healthy adult participants. Five cohorts of 8 participants each will be enrolled in the study. In each of the 5 cohorts, 6 participants will be randomized to SAR440894, and 2 participants will be randomized to placebo. Each cohort will complete the study approximately 22 weeks (150 days) from randomization through Follow-up, which accounts for the long half-life of SAR440894 and will allow for appropriate characterization of the safety, PK, and immunogenicity of SAR440894.

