### **Participant Replacement:**

Participants who withdraw prior to receiving study product will be replaced. Up to 1 participant per cohort may withdraw after dosing but before Day 112 without being replaced. Should more than 1 participant from the same cohort withdraw from the study before Day 112, they will be replaced. Any decision to replace a participant who withdraws after receiving study product will be documented in a note to file. Replacement participants will receive the same treatment as the participant being replaced.

Participants who withdraw after receiving study product will be encouraged to continue Follow-up (with participant's consent) for safety and will be asked to complete the ET visit if they do not wish to be followed per protocol. If a participant withdraws following dosing, analyses for safety, PK, and immunogenicity will be completed on blood samples already obtained.

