## 5. SAMPLE SIZE CONSIDERATIONS

No formal sample-size calculations based on testing a statistical hypothesis were performed. This study plans to randomize 40 participants. The number of participants was selected to allow sufficient evaluation of safety, and PK of the various single dose regimens to be administered in this study and is consistent with standards of practice for Phase 1 studies.

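### The SAP's 20% extrapolation guard omits AUC(0-last), its dose-normalised form, lambda-z and half-life, so an early withdrawal's truncated profile is summarised as if complete

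*SAP*

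**What the plan says.** - **Who is summarised.** SAP 6.3.2 admits to the PK Population anyone who "received a complete dose of SAR440894 and have at least one quantifiable post-dose plasma drug concentration record". No minimum follow-up is set.
- **Early leavers.** Under SAP 4.3.3, "Up to 1 participant per cohort may withdraw after dosing but before Day 112 without being replaced". For those who withdraw after dosing, "analyses for safety, PK, and immunogenicity will be completed on blood samples already obtained". SAP 6.5 imputes nothing and SAP 10.2 keeps outliers.
- **Group size.** SAP 2: "In each of the 5 cohorts, 6 participants will be randomized to SAR440894, and 2 participants will be randomized to placebo".
- **AUC(0-last).** SAP 10.2: it "is defined as the area under the concentration-time curve from dosing (time 0) to the time of the last measured concentration". No common end time is set. AUC(0-last)/Dose is the only AUC that is dose-normalised.
- **The guard.** SAP 10.2 drops AUC(0-inf), CL and Vd from the summaries if more than 20% of AUC is extrapolated or the Lambda Z criteria fail. Half-life is missing only if the Lambda Z criteria fail.
- **The Lambda Z criteria.** Adjusted R-squared of at least 0.90, and "Include at least 3 time points after" Tmax. They set no earliest time and no minimum span, and SAP 10.2 allows them to be relaxed.

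**The concern.** Followed exactly, the plan can judge a profile too incomplete to support a clearance and still put that profile's AUC(0-last) and half-life into the group geometric mean and CV. With six active participants per dose, one value carries a sixth of the log-scale mean. Exposure and half-life describe the secondary PK objective, and a dose group's figures could then reflect when someone left rather than how the drug behaves.

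A related weakness needs no withdrawal. SAP 10.1 treats concentrations that fall below the LLOQ after the first measurable one as missing. AUC(0-last) therefore ends earlier wherever concentrations reach the LLOQ earlier. Across doses from 0.3 to 20 mg/kg, that could make AUC(0-last)/Dose rise with dose when the kinetics are proportional.

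**Working it through.** The plan gives no figure to reproduce: "No formal sample-size calculations based on testing a statistical hypothesis were performed" (SAP 5), and no PK precision or bias is stated.

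**Inputs from the documents:** terminal half-life of about 4 weeks (SAP 4.2), taken as h = 28 d; six active participants per dose; the sampling times in SAP 4.5.2; the CV formula in SAP 10.1.

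**Assumed, not in the documents:** true between-participant CV of 15-40%; where used, a distribution phase with half-life 1.5-4 d and 40-50% of the initial concentration; one truncated active profile in the group.

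**1. Geometric mean AUC(0-last).** With single-phase decline and last sample T days after dosing, the truncated area relative to the full one is r = (1 - 2^(-T/h)) / (1 - 2^(-150/h)). The group geometric mean is multiplied by r^(1/6). At T = 14: r = 0.293/0.976 = 0.300, and 0.300^(1/6) = 0.818, a bias of -18%. Counting Day 1 as time zero (T = 13) gives -19%.

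| Last sample | Single phase, T = day or day minus 1 | With distribution phase |
|---|---|---|
| Day 7 | -26% to -28% | -23% to -26% |
| Day 14 | -18% to -19% | -16% to -18% |
| Day 28 | -10.5% to -11% | -9% to -10% |
| Day 56 | -4% | -4% |
| Day 84 | -2% | -2% |

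For h from 21 to 42 d (single phase, T = day), Day 14 gives -15% to -22%, Day 28 gives -8% to -14% and Day 56 gives -2.7% to -6.7%.

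**2. Geometric CV of AUC(0-last).** One of six values shifted by ln r adds (5/6)(ln r)^2/5 = (ln r)^2/6 to the log-variance s^2 = ln(1 + CV^2). The SAP formula then gives the reported CV. At Day 14 with a true CV of 25%: s^2 = 0.061 + 1.448/6 = 0.302, so the CV is 59% (x2.4). It is x2.8 at a true CV of 20%, x2.1 at 30% and x1.7 at 40%. At Day 28 it is x1.7, x1.5 and x1.4 at true CVs of 20%, 25% and 30%, and x2.1 only at 15%. At Day 56 with a true CV of 25% it is x1.09.

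**3. Half-life.** With single-phase decline, truncation causes no systematic bias. With noise-free two-phase profiles on the protocol sampling times (fast half-life/share 2 d/40%, 2 d/50%, 4 d/40%, 4 d/50%), a last sample at Day 14 gives fitted half-lives of 14.1, 11.7, 13.3 and 11.2 d against a true 28. Adjusted R-squared is 0.93-0.99, so all are accepted. Estimated extrapolation is 45-53%, so CL would be dropped while half-life is kept. The group factor is (14.1/28)^(1/6) = 0.89 to (11.2/28)^(1/6) = 0.86, or -11% to -14%. Adding 7% residual error, with a fast phase of 1.5 d/40% or 3 d/50%, gives -5% to -13% at Day 14, -2% to -6% at Day 28 and about -1% or less at Day 56. In those runs the Lambda Z criteria reject 10-35% of Day 14 profiles.

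**4. Early loss to the LLOQ.** Quantifiable to Day 84 instead of Day 150, with Day 1 as time zero: (1 - 2^(-83/28)) / (1 - 2^(-149/28)) = 0.894, or about -11% in AUC(0-last)/Dose.

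**5. Effect of extending the 20% rule.** At h = 28 d a profile ending at Day 56 has 25% extrapolated and drops out; one ending at Day 84 has 12.5% and stays. The worst retained case is (0.80/0.976)^(1/6) = 0.967, or -3.3%. With a distribution phase the estimated extrapolation at Day 56 can sit close to 20%, in which case a bias of about -4% could remain.

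**The case against.** Several points on the other side stand.

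- **Timing.** Withdrawal is tolerated at any time before Day 112. From Day 56 on, half of that window, the AUC bias is below 5% at a 28-day half-life.
- **Who withdraws.** The allowance is one per cohort of eight, two of whom are on placebo and contribute no PK. A leaver is asked for an early termination visit with a PK sample, which lengthens the profile. Against that, a replaced participant's truncated profile also stays in the PK Population, so a group can hold more than one.
- **Analyst review.** SAP 10.2 lets the PK analyst override the automatic lambda-z points after viewing the semi-log plot. That can reject a poor fit but cannot supply late samples that were never taken.
- **Visibility.** Tables 29-33 show N, minimum and maximum; Listings 2, 10 and 11 show terminations, lambda-z points and individual parameters; outliers must be discussed in the CSR. A careful reader could spot the case, but the tabulated geometric means and CVs would be unchanged.
- **Dose proportionality.** CL is dose over AUC(0-inf), is tabulated by dose in Table 28, and already carries the 20% rule. It supplies the AUC(0-inf)-based comparison. The LLOQ is not given, so early loss at low dose is a possibility only.
- **No tests are planned.** These are descriptive secondary summaries.

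**Conclusion.** The gap holds. The 20% rule protects three parameters and leaves out four that come from the same truncated profile. It matters for withdrawals of active participants up to about Day 28 and is small from Day 56 on. The AUC sizes rest on a 28-day half-life and one truncated active profile in six; the CV figures also rest on an assumed true CV.

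A reader might infer more, and the documents do not support it:
- That any tolerated withdrawal shifts the geometric means by 10-20% and doubles the CV. The AUC shift depends on the last sample time and is larger before Day 14 and smaller after Day 28. Doubling needs a last sample at about Day 14 or earlier with a true CV of about 20-30%.
- That half-life is necessarily biased. The fall of about 5-14% at Day 14 needs a distribution phase, on which the documents are silent.
- That the plan has no guarded dose comparison. CL is one.

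The primary safety analysis is untouched. The rule should be settled before unblinding.

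**What to change.** In SAP 10.2:

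1. Apply the existing rule (more than 20% extrapolated, or Lambda Z criteria not met: list, flag and exclude from statistical summaries) to lambda-z and half-life as well. Apply it also to AUC(0-last) and AUC(0-last)/Dose where the profile was cut short by early termination, so that a profile ending only because it fell below the LLOQ is not removed.
2. Add a common-window dose-normalised AUC, for example Day 0-84, beside AUC(0-last)/Dose. Fix the window before unblinding with the LLOQ in view, because a dose that is not quantifiable to the end of the window will not have the measure.

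No fixed withdrawal-day cut-off is needed. Excluding everyone who stops before Day 112, for instance, would discard Day 84 profiles that the 20% rule accepts.

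The cost is SAP wording and programming. In an affected dose group n falls by the truncated profiles, which stay in the listings.
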